symptoms AND either a low thiamine biomarker or significant improvement in or resolution of symptoms of TD after receiving thiamine supplementation^{1,17,18}. Unfortunately, the available thiamine bioassays in the US (plasma thiamine or whole blood thiamine diphosphate (ThDP)) have reference ranges that are based on thiamine status in healthy individuals and have not been validated in those with clinical diagnoses of TDDs¹. In addition, there is uncertainty in interpreting biomarker results and a lack of consensus on which biomarker is superior at distinguishing TD⁴¹. Experts suggest that whole blood ThDP normalized to RBC volume or hemoglobin concentrations should be used to ensure data from different studies are comparable¹. Measuring serum and whole blood biomarkers concurrently would be important to validate each technique in the context of clinical TD that is responsive to replenishment. Filling the knowledge gap of clear case definitions of TDDs in non-alcohol using Veterans is an important step in achieving better outcomes with diagnosis and treatment.

Acute and chronic forms of inflammation may increase the risk of developing TD. It is accepted that inflammation is a significant risk factor for developing malnutrition^{42,43}. Acute and chronic forms of inflammation are thought to contribute to the development of malnutrition through associated anorexia. Decreased caloric intake in combination with elevated resting energy expenditure (which increases the need for thiamine as a metabolic co-factor) leads to a downward spiral of depleting thiamine stores in the face of reduced oral intake. Concomitant measurement of inflammatory markers and thiamine biomarkers combined with clinical evaluation of TDDs is an open question, the answer to which is needed to further our understanding of this condition in Veterans and to develop potential mitigation strategies.

Study Aims/Objectives:

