The **objective** of this proposal is to measure the prevalence of TD and TDDs in Veterans who don't use excessive alcohol and are ill enough to require hospitalization. Additionally, we will correlate biomarkers of thiamine with signs and symptoms of TDDs which improve with thiamine replenishment. Our central hypotheses are that the prevalence of TD in this population is as high as 25% based on reports of TD in various chronic disease states^{3,12,14,19–21,24–26}, and that TDDs reversible by replenishment may occur in the “low normal” range of blood thiamine levels^{14,44}. The rationale underlying this proposal is that failing to define the prevalence of TD in this population will perpetuate the current state of underdiagnosing and undertreating TDDs which contributes to loss of independence and function. If our hypothesis is correct that the prevalence is as high as 25%, filling this knowledge gap will increase awareness of and bring action to address these problems through practice change and improved health outcomes. A parallel problem faced is that there are currently no commonly accepted clinically relevant cut-points for TD biomarkers available in the US. Clarifying the “abnormally low” biomarker cutoff levels by comparing TDDs with measured blood thiamine levels will fill a knowledge gap that has been identified¹. Through carefully defining TDDs we will fill a critical knowledge gap and assist hospitalist and rehabilitation practitioners in making the diagnosis and implementing a treatment plan. Our **long-term goal** is to increase recognition and treatment of TDDs in Veterans by describing the clinical syndromes in non-alcoholics, as well as understand the root causes of TDDs. This will improve long-term health outcomes for Veterans with acute and chronic illnesses and help them maintain independence and function. We will test our central hypothesis and attain our objectives via the following **specific aims**:

Aim 1: Utilizing a prospective cohort study design, determine the prevalence of TD, as defined by whole blood and plasma thiamine levels and symptom responsive disease, and describe social and medical factors predisposing to TD in consecutively hospitalized non-alcoholic medicine patients.

Hypothesis 1: The prevalence of TD in hospitalized Veterans who do not use excessive alcohol is between 10 and 25%, much higher than the general population estimate of less than 3%.

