Aim 2: Through an open label treatment study, we will define thiamine deficiency disorders (TDDs) as cases with low or “low normal” thiamine levels and symptoms of TD that improve with thiamine replenishment. Hypothesis 2: The current bioassays of thiamine do not accurately define TDDs and individuals with results the “low normal” range will show symptom improvement with thiamine replacement.

Aim 3: Utilizing a nested case control study design, determine if acute and chronic inflammatory conditions with elevated biomarkers of inflammation increase the risk of developing TDDs. Hypothesis 3: Acute and chronic forms of inflammation cause oxidative stress which increase basal requirements for thiamine as a metabolic cofactor and increase the risk of developing TDDs.

Study Population:

We anticipate 300 patients will be enrolled in this study with an age range of 18 and older. There will be no exclusions due to gender, race, age, or ethnicity. We will endeavor to include women and minorities to the extent possible based on the inpatient population which historically has been predominantly male (95%) and white (90%). All subjects recruited for this study will be Veterans admitted to inpatient units at VA Sierra Nevada Healthcare System hospital (single site recruitment). There will be no minor children participating. The health status will be compromised from mild to severe due to the nature of being hospitalized. We will not include adults unable to consent (those who are cognitively impaired with Impaired Decision-Making Capacity). We will not enroll pregnant women as we do not admit them to the VA hospital due to lack of maternity services.

Inclusion criteria:

- anyone age 18 or older requiring full hospital admission to the medical service.

Exclusion criteria:

- excess alcohol intake as defined by the National Institute of Alcohol Abuse and Alcoholism as more than 14 standard drinks per week for men less than age 65, or more than 7 drinks per week for women or men 65 years of age or older
- unable to consent due to impaired decision making capacity.
- veterans who live more than 75 miles from the study site as that would likely hinder their ability to attend follow up visit 3.
- Veterans who suffer from quadriplegia because they cannot participate in the physical assessments
- Veterans taking thiamine supplements

Vulnerable Populations:

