Measurements: The **primary outcome** of this study is to measure the prevalence of TD as defined by abnormally low or low normal thiamine biomarkers combined with symptoms that respond to thiamine replenishment. **Secondary outcomes** will include describing demographic, clinical, and nutritional characteristics among those with and without TDDs. A TDD will be defined as an acute condition with symptoms that are known to be due to TD and that improve with adequate thiamine replenishment.

Statistical analysis/power calculations: Our primary endpoint is the prevalence of TDDs which we will compute as the proportion of TDD cases over the total number of subjects enrolled. Given the feasibility of this study and our patient population, we believe we can enroll and follow 300 subjects over a one-year enrollment period with an anticipated drop-out rate of 15%. Current best estimates for TD in similar populations are approximately 25%^{19,24,27}. Such an enrollment would provide us with a precision of TDD prevalence of +/- 5.4%. A sample size of 300 and estimated drop out of 15% leaving 255 subjects would provide us with 81% power to detect an 8% absolute difference from this expected prevalence. To explore differences in demographic, clinical, and nutritional characteristics among those with and without TDDs, continuous variables will be compared by T-test unless parametric assumptions are not met in which case a Kruskall-Wallis test will be used. Categorical variables will be evaluated through Chi-square or Fishers exact test depending on assumptions being met. We will estimate prevalence rate ratios for association factors. If the prevalence is achieved, we estimate that we would have adequate numbers to identify a range of different rates of exposure variables among TDD and non-TDD patients. For example, with 63 TDD and 192 non-TDD patients and a 10% rate of a given explanatory variable, we would have 80% power to detect prevalence rate ratios of ~2.5 and higher in bivariate analyses.

15.2 Open label treatment study to develop standardized case definitions of treatment responsive TDDs and correlate with thiamine biomarker levels to determine clinically relevant cut-points of those biomarkers.

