Measurements: The **primary outcome** of this arm is to describe the prevalence of treatment responsive TDD symptoms in the hospitalized Veteran population. The **secondary outcome** is to explore cut-points of thiamine biomarkers that can be utilized to diagnose TDDs with more sensitivity than current clinical laboratory limits.

Statistical analysis: Descriptive features of treatment responsive TDD patients will include frequencies of symptoms, physical exam findings, and functional disability compared to patients without TDDs. We will describe each case's initial signs and symptoms and improvements. To better define the thiamine levels that differentiate thiamine responsive from thiamine non-responsive symptoms, the levels of thiamine will be compared between groups using Kruskal-Wallis test corrected for multiple comparisons. For the two thiamine biomarkers, the optimal cut-point to distinguish between thiamine responsive and thiamine non-responsive symptoms will be determined by applying the Liu method⁴⁷ to maximize the product of the sensitivity and specificity. Based on the cut-points, thiamine levels will be dichotomized into lower and higher or equal to the cut-point and the area under the receiver-operating curve (AUC), the sensitivity, specificity, positive and negative predictive values, and the likelihood ratio will be computed. These cut-points will be compared to that of the current laboratory reported abnormal cut-points. For this aim the power to identify discriminating cut-points will be dependent up on the prevalence of the treatment responsive disorder and the distribution of thiamine levels. Under conservative assumptions (alpha 0.05, beta 0.80) and a 2 to 1 ratio of negative responders to positive responders at a given thiamine cut-point level, we would need 19 responders and 38 non-responders for a given symptom to estimate an area under the curve (AUC) of 0.725 compared to a null AUC of 0.50. While there is no information to inform the reasonableness of these parameters, we believe we will have reasonable ability to explore thiamine level cut-points for treatment responsive TDD for this exploratory aim.

4.3 Nested case-control study to determine if inflammation is associated with the presence of TD in hospitalized veterans.

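### Hypothesis 1 sets a composite prevalence (low or low-normal level plus response) against an undefined under-3% benchmark, so the contrast is not like for like and its bias has no known direction

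*Combined protocol and SAP*

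**What the plan says.** **The contrast.** Hypothesis 1 (Study Aims/Objectives) puts TD prevalence in hospitalised Veterans without excess alcohol use "between 10 and 25%, much higher than the general population estimate of less than 3" per cent. The under-3% figure also appears twice in the Background. Nowhere is it tied to an assay, a cut-off, a symptom requirement or a response requirement.

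**The definitions of a case.** The protocol uses several:

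- Aim 1: "determine the prevalence of TD, as defined by whole blood and plasma thiamine levels and symptom responsive disease", with no cut-off and no mention of low normal.
- Aim 2, for thiamine deficiency disorders (TDDs): "cases with low or “low normal” thiamine levels and symptoms of TD that improve with thiamine replenishment".
- Section 15.1, primary outcome: "prevalence of TD as defined by abnormally low or low normal thiamine biomarkers combined with symptoms that respond to thiamine replenishment". The same section then computes the primary endpoint as TDD cases over all enrolled, and defines a TDD by symptoms and improvement without naming a biomarker.
- Background: "symptoms AND either a low thiamine biomarker or significant improvement in or resolution of symptoms of TD after receiving thiamine supplementation".
- Section 4.3 (nested case-control study): treatment-responsive TD, or a level abnormal by the clinical laboratory's standard.

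**The low-normal band.** The Background says that the available US assays "have reference ranges that are based on thiamine status in healthy individuals". The protocol gives no numerical bounds for low normal. Section 15.2 looks for cut-points that "diagnose TDDs with more sensitivity than current clinical laboratory limits".

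**The concern.** Low-normal results lie inside a reference range built on healthy people. Admitting them as potential cases enlarges the pool from which cases are drawn, and the protocol does not say that the under-3% estimate was built the same way. Hypothesis 2 and section 15.2 argue that current laboratory limits miss true cases. If the under-3% figure rests on such limits, it too could rise under the study's definition.

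Section 15.1 plans no prevalence of laboratory-low thiamine. Neither the cut-point comparison in 15.2 nor the combined group in 4.3 supplies one. A reader of the final report could therefore not tell how much of a gap between the study's figure and 3% reflects hospitalised Veterans and how much reflects the case definition. What is at stake is the interpretation of Hypothesis 1, not the sample size.

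**Working it through.** **1. The plan's own figures.** With 300 × 0.85 = 255 completers and an expected prevalence of 25%, the 95% half-width is 1.96 × √(0.25 × 0.75 / 255) = 5.3 points (Wald) or 5.5 points (Clopper-Pearson). The plan states 5.4. Power for 25% against 33%, assuming two-sided alpha 0.05 (15.1 states none), is 81.9% by the normal approximation, 80.5% by arcsine and 77.3% exact. The plan states 81%. These figures are close enough and are not in dispute.

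**2. Sampling error is not the obstacle.** No test against 3% is planned. If one were run with n = 255 (exact binomial, two-sided 0.05), 14 or more cases (14/255 = 5.5%) would reject 3%, with 99.7% power at a true 10%. Whether an excess can be claimed depends on comparability.

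**3. How far the low-normal band could move the result.** The only cohort for which the protocol gives both shares is the stroke rehabilitation cohort in the Background: 14% low and a further 49% low normal. Let L be the laboratory-low share (all assumed to be responders), N the low-normal share, and q the share of low-normal patients who have symptoms and are rated as improved.

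Counted prevalence = L + N × q

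Take L = 3%, no higher than the general-population ceiling, and N = 49%:

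- To reach 10%: q = (0.10 − 0.03) / 0.49 = 14.3%
- To reach 25%: q = (0.25 − 0.03) / 0.49 = 44.9%

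Neither N nor q is known for this population. With L fixed at 3%:

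| N | q = 20% | q = 50% |
|---|---|---|
| 10% | 5.0% | 8.0% |
| 20% | 7.0% | 13.0% |
| 30% | 9.0% | 18.0% |
| 49% | 12.8% | 27.5% |

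Improvement is a two-category rating made at Visit 3 (section 10.3). Treatment is open label with no control group, in patients recovering from an acute illness. A q of 14% to 45% cannot be ruled out in advance.

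**4. The opposite direction.** On the stroke split as it stands, the laboratory-low share regardless of symptoms is 14%, already above 3% and inside 10-25%. If one response rate r applies to both bands, the composite is (0.14 + 0.49) × r = 0.63r. This falls below 14% whenever r is under 14/63 = 22.2%. At r = 20% the composite is 12.6%; at r = 40% it is 25.2%. The low-and-responsive part, 0.14r, stays above 3% when r exceeds 3/14 = 21.4%. The composite can thus lie on either side of the laboratory-low figure.

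**The case against.** Four points on the other side have force.

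- **Low normal is not in Hypothesis 1 or in Aim 1.** This is correct. It enters through Aim 2 and the 15.1 primary outcome. But 15.1 is the analysis that answers Aim 1, so its definition governs the figure that will be reported.
- **Requiring response narrows the definition.** This is also correct. A healthy person with a low-normal level and no responsive symptoms would not be a case. A reader might infer that the definition must inflate the result; the documents do not support that, because the net direction is unknown. The mismatch remains.
- **A real excess is plausible.** The 14% in the stroke cohort shows this. A reader might infer that the excess is purely a matter of definition. Step 3 shows only that it could be, under an assumed 3% low share. Reporting the laboratory-low share would help to settle the question.
- **The under-3% figure is a background benchmark with no planned test.** This stands, and it confines the point to interpretation. The benchmark is nevertheless written into the hypothesis.

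It is also tempting to say that laboratory-low prevalence is the only valid comparator. The documents do not go that far. The Background applies the under-3% figure to TD and TDDs together, so it may include clinical disease, and the definitions behind the 10-25% range are not given either.

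**Conclusion.** The point holds as one of comparability. The planned primary figure and the under-3% benchmark are not shown to measure the same thing, and the plan produces no figure that could be matched to a laboratory-based benchmark. The direction of bias cannot be determined from the documents.

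On the protocol's 49% low-normal share and an assumed 3% laboratory-low share, all responders, an improvement rating in 14% to 45% of low-normal patients would be enough to produce 10% to 25% without any excess of laboratory-low thiamine. This rests on carrying a stroke rehabilitation cohort's plasma results over to general medical inpatients, and the improvement shares are illustrative. It shows what is possible and is not a forecast. Sample size and stated power are unaffected.

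**What to change.** 1. In 15.1, add the proportion of Veterans below the laboratory lower limit, regardless of symptoms, for plasma thiamine and for whole blood thiamine diphosphate separately. Use Veterans with a result as the denominator and give a 95% CI.
2. Report the low-or-low-normal plus response prevalence separately, split into its low and low-normal parts.
3. State the definition (assay, cut-off, symptom and response requirements) behind the under-3% figure and behind the 10-25% range. Compare only the study figure that matches. Make no claim of excess over the general population for the composite unless it matches.
4. Reconcile the TD and TDD definitions in the Background, Aims 1 and 2, and sections 15.1 and 4.3, and reword Hypothesis 1 to fit.

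The cost is wording and a few more lines of reporting. Both assays are already ordered at Visit 1, so no new data, visits or participants are needed. The downside is that the figure set against 3% may be less favourable than the composite.

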10 STUDY INTERVENTIONS

Table 3: Study procedure schedule of evaluations

	Visit 1- early hospitalization	Visit 2 – late hospitalization	Visit 3 – after 2 weeks of thiamine repletion
Chart review for social and medical histories	X		
Symptom and function survey		X	X
Targeted physical exam		X	X
Nutritional history		X	
Lab draw for thiamine biomarkers	X		X
Blood draw for prealbumin , others as needed	X		
Thiamine repletion	X ¹	X ²	

1. For select patients with WE or severe symptoms of thiamine deficiency 2. all others

10.1 Visit 1 – initial hospital encounter: The Veteran's chart will be reviewed for acute and chronic medical problems, habits, and social history. We will schedule lab testing (as described below) to coincide with routine morning blood draw to avoid additional phlebotomy. For those who present with symptoms of Wernicke's encephalopathy (WE) which requires urgent parenteral thiamine replacement, we will perform our history and exam promptly and advise the primary inpatient treatment team to initiate therapy if they meet the Caine criteria⁴⁶ for WE. For all others who do not have evidence of WE, we will proceed to visit 2.

Thiamine biomarker and other micronutrient assessment: Fasting plasma thiamine levels and whole blood ThDP will be ordered for collection by lab personnel as soon as feasible after consent is obtained from the Veteran. We will also order blood levels of vitamins B12, D, and folic acid as well as prealbumin if not done via routine care within the preceding four weeks. In addition, we will extract albumin, complete blood count, and magnesium as ordered by the primary team as part of routine care. There will be no genomic sequencing, in whole or in part, as part of this analysis. Blood specimen will be collected as part of routine medical care by laboratory personnel. Lab tests not routinely run in our local laboratory will be sent out to reference labs per the usual practice of the Department of Pathology. There will be no direct handling of blood specimen by the research team. Results of the lab tests will be available in a participant's electronic medical record and will be extracted by the study coordinator and stored in a de-identified database. If they have been prescribed thiamine replenishment and the thiamine lab values are lost, we will include the remaining data gathered in the study.

10.2 Visit 2 – second hospital encounter: Following stabilization of the acute medical condition(s) for which they presented, the Veteran (and caregiver if the Veteran agrees) will be interviewed and examined by the study's PI or trained advance care practitioner using a standardized checklist of signs and symptoms of TD. We will delay this portion of the assessment until the primary treating team affirms their acute condition has stabilized to avoid misclassification of symptoms from the acute illness with those of TDD. In most cases we anticipate this will occur just prior to hospital discharge. For Veterans with symptoms suggestive of TD, we will provide a prescription for thiamine replacement 100 mg orally daily for two weeks (see **Standardized physical examination and related data**).

Nutritional history: Study personnel will perform a dietary history to adequacy of thiamine intake, recent changes in appetite, food intake or any social or medical risk factors for malnutrition. We will review medical records for acute and chronic medical illnesses that may predispose to malnutrition.

Symptom and function survey: The patient interviews will include questions about the following: acute or worsening symptoms in the following categories: neuropsychiatric (including memory loss, personality or behavior change, psychosis, mood changes, seizures), polyneuropathy (to include muscle weakness, loss of deep tendon reflexes, neuropathic pain, or sensory loss), GI dysfunction (including dysphagia, anorexia, nausea, vomiting, gastroparesis, or constipation), and cardiovascular manifestations (such as palpitations, tachycardia, dyspnea, pulmonary or peripheral edema). We will review recent trends in ability to carry out Basic Activities of Daily Living (ADLs) and Instrumental Activities of Daily Living (IADLs). We will determine if there are symptoms of adult failure to thrive such as weight loss, decreased appetite, inactivity, poor nutrition, depression, loss of functional status as defined by loss of ability to do ADLs or IADLs. We will also ask about medication compliance with both prescribed and over the counter medications and supplements.

Standardized physical examination and related data: We will perform targeted exams for signs of TDDs including mental status exam using the Montreal Cognitive Assessment (MoCA); delirium screen using the 4AT

clinical test; ophthalmoplegia and nystagmus using the “H” test; evaluations of ataxia, peripheral neuropathy, deep tendon reflexes, and muscle strength using the Medical Research Counsel Adaptation B scale. We will assess for signs of cardiovascular dysfunction such as pulmonary or peripheral edema and tachycardia, and GI signs such as decreased bowel tones. We will assess physical signs of malnutrition including muscle and fat loss and trends in body weight. We will review any existing radiologic studies for evidence of abnormal brain imaging, echocardiogram results, pulmonary edema, or ileus for example.

For patients with severe symptoms such as inability to ambulate, or WE, we will advise the primary treatment team to begin high dose intravenous (IV) thiamine replenishment at 400 mg every eight hours for nine doses while inpatient. In this group we will then prescribe oral thiamine 100 mg once a day after IV therapy is complete until visit 3. For patients with mild-moderate symptoms that could be due to TD, the research pharmacist will process and dispense oral thiamine 100 mg once daily at hospital discharge. If the patient is discharged when the research pharmacist is not at the hospital, the research pharmacist will mail it to the patient on the next business day. Patients who are discharged to skilled nursing facilities, or any other rehabilitation facility, will be contacted by the research team and be medically advised to supplement the patient with oral thiamine 100 mg. We anticipate return of lab biomarker results 7-10 days after they are drawn at which point any individual not identified by clinical screening to have TD will be contacted and oral replenishment initiated. As with the symptom and function survey we will record these findings on a government furnished computer with a paper record as backup.

10.3 Visit 3 – follow-up of symptomatic Veterans after empiric thiamine treatment. All Veterans with low biomarkers OR low normal biomarkers and clinical symptoms of TDDs that were initiated on replacement will be seen at a follow-up visit 3 after two weeks of thiamine replacement. We will repeat the symptom and function survey and repeat the standardized physical assessment. We will categorize changes in symptoms and signs as *no or minimal improvement, or noticeable improvement*. We will re-order thiamine biomarkers to assess for increases in levels. We will recommend continued dosing with thiamine 100 mg daily thereafter for any Veteran with improvement in their symptoms and update their medical record to include thiamine deficiency in their problem list. If a participant failed to complete the 2 weeks of replenishment, we will provide another 2-week course of replenishment and reschedule this visit.

Study Duration/ Study Timeline:

See Table 3. We expect visit 1 will not take substantial time for the Veteran. Visits 2 and 3 will take between 60 and 90 minutes each. For Veterans without symptoms of TD, their participation will be complete after visit 2, before discharge from the hospital. For Veterans with symptoms of TD their participation will be complete after taking thiamine for 2 weeks and attending visit 3. We anticipate the study will end 24 months.

Study Endpoints:

Our primary endpoint will be determining prevalence of TD in our Veteran population. We do not anticipate stopping the study before 300 Veterans are recruited. Thiamine supplements are very safe with few side effects, so we do not anticipate stopping early for safety concerns.

Study Locations:

The study will be conducted at the VA Sierra Nevada Healthcare System Hospital inpatient units at [name]. Follow up visits will occur on the ground floor of the hospital in the research department exam rooms.

International Research:

We will not be conducting this research in international locations.

Participant Compensation:

Those that agree to participate will be compensated \$30 for visits 1 and 2 and \$200 if they attend visit 3 after discharge.

Economic Burden to Participants:

Veterans will not incur any costs because of participating in this study. Those that attend the follow up visit will incur the cost of transportation, but this will be mitigated by the \$200 compensation.

Risk to Participants:

The principal risks to the patient are those associated with phlebotomy, namely discomfort and bruising associated with a needle stick. All efforts will be made to combine our tests with routine phlebotomy draws ordered by the primary treatment team. In some cases, additional time spent with investigators performing interviews and physical exams may cause psychological distress. In cases where thiamine is prescribed to treat suspected thiamine deficiency, there are rare instances of adverse reaction to parenteral thiamine such as anaphylaxis, pruritis, and local inflammation. Oral thiamine is typically well tolerated, the main difficulty is possibly having trouble swallowing tablets. There are extremely rare instances of side effects such as flushing, hives, itching, weakness, sweating, nausea and restlessness.

Protection Against Risk: The risk of bleeding or bruising due to phlebotomy will be mitigated by combining our specimen collection with routine collections placed by the primary treatment team to avoid extra phlebotomy. Only qualified personnel will draw blood. For psychological stress suffered, the Veterans will be assured they may refuse and withdraw from the study at any time if it becomes too burdensome. For instances where parenteral thiamine is ordered, it will be in a hospital setting where prompt medical attention is available should anaphylaxis or other side effects occur. For Veterans prescribed oral thiamine replacement who have difficulty swallowing tablets, a pill crusher will be provided. Any adverse reactions to parenteral or oral thiamine repletion will be recorded and replenishment discontinued.

Confidentiality Risks: Every effort will be made to keep all research information obtained from blood samples confidential, but absolute confidentiality cannot be guaranteed. Laboratory data obtained from blood samples will appear in the medical record for review by VA medical providers. The research information obtained as a result of participation in this study will be included in the medical record and may be given to primary care doctors. Information from which participants may be personally identified will be maintained in a confidential, locked file and will not be disclosed to third parties except with participant permission or as may be required by law.

A progress note will be included in the patient's medical record for all research subjects who receive research procedures or interventions as inpatients or outpatients at VA medical facilities that are either used in or may impact the medical care of the research subject at a VA medical facility or at facilities VHA Directive 1200.05(2); 1/7/2019.

Benefits to Participants:

The potential benefits of research to subjects and others include improvement in thiamine deficiency symptoms where thiamine replenishment is prescribed. Other potential benefits include improved health outcomes for all Veterans by increasing awareness of the scope of the problem of thiamine deficiency in those hospitalized and mitigation of this health problem. Thiamine deficiency is currently thought to be rare in the United States in people who do not drink excess alcohol. However, there is evidence that demonstrates it is not rare and is often overlooked as a cause of weakness, falling, memory loss and other problems that cause debility. The results of this study will help us understand the magnitude of the problem in vulnerable Veterans who are ill enough to be hospitalized. We anticipate this knowledge will increase awareness of thiamine deficiency as a problem for hospitalized adults and treatment will improve quality of life for Veterans.

Privacy of Participants:

We will apply for a HIPAA waiver to initially review a potential Veteran participant's chart for exclusion criteria. This will be a very limited chart review. Once eligibility is determined, the Veteran will be approached his/her private or semi-private hospital room. If the Veteran is in a semiprivate room and requests the study interview and exam occur in a private room, every effort will be made to move them to a private room for the study procedure.

Data Management and Confidentiality:

All participants will be assigned a unique ID upon their initial screening appointment. The unique ID will be randomly generated to ensure no identifying information is used to reference participants throughout the course of the study. A linking database will then be established by the PI using excel that will allow for the investigator to re-identify subjects if the need arises (Serious Adverse Events (SAE), Unanticipated Problems (UP), etc.). Only the PI and delegated members as of the research team will have access to the linking database which will be password protected and remain on the VA premises at all times. All data collected and stored in the repository will be coded using unique IDs to ensure the identify of subjects cannot be readily ascertained. Only RDC/IRB approved members of the study team will have access to the data repository which will be password protected and stored within the VASNHC servers on the VHA network.

Data for this study will be used for research purposes only, stored securely within the VA. In the event of an accidental disclosure or breach of personally identifiable information (PII), the facility privacy officer will be notified as soon as the PI is aware of the issue. All telephone conversations involving PII will be led by IRB-approved research staff and conducted in private confidential spaces either within a VA office or at an approved teleworking location. A deidentified dataset will be created to be shared with former VA research staff member who is now a community member without VA affiliation due to external circumstances. She wishes to continue assisting with data analysis when needed. De-identified data which may be shared with non-VA staff will be stripped of all Protected Health Information (PHI), including all 18 HIPAA PHI identifiers, per the Safe Harbor standard of de-identification under HIPAA. De-identified data may be sent electronically through IRBnet.org or VAIRRS to IRB-approved staff for safety and protocol deviation reporting. All data will be stored and maintained in accordance with VHA Records Control Schedule (RCS) 10-1. Deidentified group or aggregate data will be reported in research publications or at scientific conferences following privacy officer approval; however, no identifiable data will be included. Identifiers will be removed from the data and after such removal, the information could be used for future research studies or distributed to another investigator for future research studies without additional informed consent from the subject or the legally authorized representative. No biospecimen will be retained or distributed to other researchers. While this study will store de-identified data for future research, the use of this data will not affect the rights or privacy of participants. The research team will ensure privacy and confidentiality of all participants is maintained throughout the study.

Any data recorded on paper will be stored in a locked file cabinet inside the locked research offices at the VA.

Provisions to Monitor the Data to Ensure the Safety of Participants

Thiamine repletion is considered very safe with extremely rare side effects (less than 1%) as such we do not anticipate and serious adverse events. Side effects of intravenous thiamine are reported to be flushing, restlessness, sweating, itching, hives, nausea, gastrointestinal bleeding, anaphylaxis, angioedema, weakness, and pulmonary edema. Oral thiamine (the formulation used in this study) may have similar side effects although far less commonly than the rare effects noted with IV thiamine. Thiamine is an approved treatment for Wernicke's encephalopathy and has been used widely in medical practice since the 1950's. We will not be using any new formulations or doses outside of current recommendations for the treatment of symptoms of thiamine deficiency. The PI, study coordinator, and Health Systems Specialist will monitor Veterans prescribed thiamine repletion and report any new or unusual symptoms to the IRB.

Data and Specimen Banking

During screening and recruitment, data will be on paper and stored in the research department in a locked cabinet behind locked department doors, building 1 room C3334. Only the PI and study personnel will have access to these records. Once a veteran agrees to participate and is enrolled in the trial, all subsequent data will be stored electronically on the restricted research drive. For veterans who are screened but not enrolled, their records will be maintained for 7 years in accordance with VHA Records Control Schedule (RCS 10-1). All study data will be stored both on paper in locked filing cabinets and electronically in the data collection tool REDCap. We will not be storing any specimen.

Data will be stored electronically in \\r01renhsm01.r01.med.va.gov\research\Principal Investigators\[name]\Thiamine Research and in REDCap (varedcap.rcp.vaec.va.gov). Data that will be stored electronically include:

1. Unique study ID number with patient name and last 4 of social security number and telephone number in a master key spreadsheet, to be separated from the remainder of the data.
